5.4 SCREEN FAILURES

A patient will be defined as screened after the signature of the informed consent and the assignment of a Screening Number. The preparation of an eCRF will be done regardless of the completion of all the screening procedures. Patients that will go through screening but will not be enrolled will be considered a screen failure. Patients may be re-screened on a case-by-case basis after reviewing it with the Sponsor.

In this study a screen failure rate of about 20% was considered on the basis of the previous clinical experience obtained with the NGF0121 - PROTEGO-1 study, which also enrolled highly symptomatic dry eye patients. We expect to screen approximately 350 subjects in order to have 291 subjects enrolled.

The sample size remains at 291 subjects independent of screen failures.

5.5 LIFESTYLE CONSIDERATIONS

5.5.1 Meals and Dietary Restriction

No new drastic changes to diet adding fish oil supplements, flaxseed supplements, omega-3 supplements since they could potentially alter fTBUT.

5.5.2 Caffeine, Alcohol, Tobacco, and Other Habits

Patients should limit smoking tobacco since tobacco smoke is a known eye irritant, it may worsen dry eye disease and confound results. Patients should also avoid exposure to second-hand smoke for prolonged periods.

5.5.3 Physical Activity

No particular restrictions are required.

5.5.4 Other Activities

Avoid heavy use of eye make-up along lash lines like eyeliner and mascara since those could artificially alter fTBUT.

6 TRIAL INTERVENTION AND CONCOMITANT THERAPY

6.1 DESCRIPTION OF TRIAL INTERVENTION, DOSING AND ADMINISTRATION

Treatments are described in the table below.

Table 4: Description of treatments

Treatment Name	Vehicle IMP	IMP 1	IMP 2
Active Ingredient	none	rhNGF	rhNGF
Quality Control	Dompé Farmaceutici S.p.A. (Italy)		
Dose (daily)	0 mcg/mL Vehicle	CC1 mcg / eye/day 1 drop of CC1 mcg/mL /eye TID	CC1 mcg/ eye/day 1 drop of CC1 mcg/mL/eye TID
Pharmaceutical form (see §2.2)	CC1 vehicle + diluent	CC1 rhNGF + diluent	
Formulation	ophthalmic solution (reconstituted eye drops)		
Regimen	1 drop (40mcL) both eyes TID (Every 6 h)	1 drop (40mcL) both eyes TID (Every 6 h)	1 drop (40mcL) both eyes TID (Every 6 h)
Route of Administration	Ocular	Ocular	Ocular
Stability & storage of the eye drop solution	CC1 pC Keep it protected from sunlight and heat	CC1 pC Keep it protected from sunlight and heat	CC1 pC Keep it protected from sunlight and heat
Stability & storage of the pharmaceutical form	CC1 pC Keep it protected from sunlight and heat	CC1 pC Keep it protected from sunlight and heat	CC1 pC Keep it protected from sunlight and heat

6.1.1 Non-Investigational Medicinal Product

The Non-Investigational Medicinal Product (NIMP) that should be used in the follow-up period is shown in the table below.

Table 5: Description of NIMP

Treatment Name during Follow-up Period	NIMP (Preservative free artificial tears)
Dosage (daily)	3 drops / eye
Regimen	One drop in each eye, TID (Every 6 h)
Formulation	Preservative free, sterile solution, single use/multi-use
Route of administration	Topical ocular (eye drops)

6.1.2 Trial Intervention Dose Modification

No dose modification is anticipated at this time.

6.2 RATIONALE FOR TRIAL INTERVENTION

The trial tests two CCI concentrations of a new CCI rhNGF formulation (C mcg/mL or C mcg/mL) in patients with DED. This new formulation not only allows to CCI the concentration of rhNGF down to C mcg/mL, but also allows the storage at CCI °C of the ophthalmic solution containing the active principle, hence reducing patient burden with respect to storage and handling of IMP. The rationale for the selection of the two proposed CCI concentrations of rhNGF stems from both manufacturing and clinical rationales. Specifically, from a manufacturing standpoint, the development of the new CCI formulation opens the possibility to test a rhNGF concentration as CC as C mcg/mL, which will provide the opportunity to test the minimally effective dose in the target population. From a clinical standpoint, both the C and C mcg/mL proposed concentrations can reasonably be expected to be safe and effective in the target population based on previous clinical trial experience with different rhNGF concentrations. Specifically, starting from the first phase 2 clinical trial performed in Europe (REPARO, NGF0212) in patients with Neurotrophic Keratitis, both the C and C mcg/mL were proven safe and effective on corneal healing. The following clinical trials in DED also tested concentrations of rhNGF up to C mcg/mL. In the DED studies we observed efficacy on tear function but a suboptimal tolerability of the higher concentrations tested (for example, 48% patients reported eye pain in NGF0121 - PROTEGO-1, up to 63.5% in NGF0118, and 42% in NGF0216). Therefore, the new formulation of rhNGF was prepared to allow a CCI concentration with the goal of consequently CCI

CCI TEAEs for patients, while maintaining efficacy on DED signs. The C mcg/mL dose group has the potential to show clinical benefit since an earlier open-label study (NGF0213) in dry eye patients demonstrated that with doses as CC as C mcg/mL (obtained by on-site dilution of the C mcg/mL formulation) treatment (BID, 4 weeks), patients showed improvement in both SANDE and Schirmer scores up to 4 weeks post-completion of treatment (day 56). Hence, this trial aims to determine the safety and efficacy of 2 CCI concentrations of rhNGF in dry eye patients.

TID and not BID dosing was selected based on evidence that TID dosing demonstrated sustained improvement in symptoms (SANDE scores) for up to 12 weeks after completion of treatment (week 16), unlike BID dosing, which was unable to maintain improved symptoms beyond the week 4 end-of-treatment time point (NGF0118).

Furthermore, a shorter duration of treatment was selected (4 weeks) with TID dosing based on recent studies with 4-week long treatment using TID dosing (NGF0118, NGF0121 - PROTEGO-1) that demonstrated efficacy in patients with moderate to severe dry eye. This is a reduction in both duration and dosing in comparison to an earlier study where dry eye patients were treated for 8 weeks with six times a day dosing (NGF0216) at an rhNGF concentration of C mcg/mL.

Topical ophthalmic route through eye drops was selected since PK studies demonstrated that there is minimal systemic absorption of rhNGF through this route of drug delivery.

6.3 PREPARATION, HANDLING, STORAGE AND ACCOUNTABILITY

The Study Products consists of:

- A sterile CCI preparation containing vehicle or CCI mg/vial of rhNGF, packaged in a glass vial and administered after reconstitution with
- 1 mL or 2 mL of diluent contained into a separate glass vial.

The Study Products are reconstituted using an adapter and a sterile syringe and administered using a sterile pipette.

After reconstitution the Study Product is a sterile solution for ocular administration at the following concentrations as active ingredient:

- IMP 1: rhNGF C mcg/mL (2 mL diluent)
- IMP 2: rhNGF C mcg/mL (1 mL diluent)
- IMP (Vehicle): rhNGF 0 mcg/mL (Vehicle in 1 mL or 2 mL diluent)

Store the products before and after reconstitution at CCI °C protected from sunlight and heat. Once the CCI product is reconstituted in diluent, the solution should not be shaken since agitation may cause foaming. The eye drop solution should be prepared daily and used only for 1 day, kept at CCI °C sheltered from sunlight and heat.

The clinical labeling of the investigational medical product (IMP and vehicle) will be done in a manner that protects the masking of the study medications. It will include a statement of

caution and describe particulars applicable to regulatory requirements (e.g.: kit number, protocol number, storage conditions, name and address of the sponsor, statement that the product is for investigational use only, etc.). A clinical labeling with similar statements will be also provided for the Study Product vehicle to be used during the Run-In Period.

The Pharmacist and/or Investigator will be responsible for receipt, proper storage, dispensation reconciliation, usage, and final disposal of remaining Study Products (where applicable). The Study Products must be stored at **CCl** °C sheltered from sunlight and heat at the investigational sites, in an appropriate locked room accessible only to the pharmacist, the Investigator, or a duly designated person. A data logger will accompany the Study Products on shipment. It is essential that the investigational sites verify the temperature excursion during shipment vs. the acceptable storage conditions (**CCl** °C), in order to identify potential stability concerns during shipment. These must be immediately communicated to the Sponsor that will decide upon appropriate actions to be taken. Any deviation from the recommended preparation, storage and handling conditions of the Study Products should be immediately reported by the pharmacist to the Sponsor and to the Investigator, and the use of the Study Product should be suspended until the Sponsor has given authorization for its continued use. The Study Product supplies are to be used only in accordance with this protocol. The Investigator will not use any Study Product samples for other purposes (e.g., treating patients or deviating from the protocol with regard to dose regimen, duration of treatment, etc.). Under no circumstances will the Investigator give any Study Product samples to a third party.

Upon receipt of the Study Products (including Vehicle) and NIMP at the site, the investigator will log the receipt of the Study Products (including Vehicle) and NIMP and store as per the storage instructions provided with the Study Products (including Vehicle) and NIMP kits. Study Products (including Vehicle) and NIMP will be dispensed to the patients by qualified and delegated site staff according to the study requirements and as listed in the Schedule of Activities (Table 1). The site personnel will maintain an accountability log for Study Products (including Vehicle), documenting the receipt, dispensation, return, and destruction of all Study Products (including Vehicle). The site personnel will also maintain an accountability log for NIMP, documenting the receipt and dispensation of NIMP.

To establish and maintain accountability of Study Products (including Vehicle) and NIMP, the Pharmacist and/or Investigator will confirm the receipt of the Study Products (including Vehicle) and NIMP supply in writing by signing and dating standard drug accountability forms. The Pharmacist and/or Investigator will keep a cumulative inventory and dispensing records and will maintain all supplies under adequate security. An accurate drug disposition record will be kept, specifying the date and amount dispensed to each patient.

Adequate record of receipt and use or loss of drug will be retained. This inventory record kit must be available for inspection by the Sponsor and regulatory inspection at any time. Copies of this record will be provided to the Sponsor by the CRO throughout the duration of the study.

During the course of the study and until its conclusion, the Investigator will complete the drug accountability forms. Partially used or unused study drug boxes will be verified by the CRO

delegated Monitor. The partially used and unused study medication will be shipped to the Sponsor or will be destroyed after authorization by the Sponsor or by an authorized company according to GCP regulations.

Study Products' preparation and administration instructions will be provided separately to the site and to the patients.

Study products will be provided to the patients as a biweekly kit containing 14 daily boxes. Each daily box will contain one vial of CCI Study Product and one vial of diluent solution. In the bi-weekly kit will be also included an appropriate number of vial adapter, sterile wipes and empty luer lock syringes to ensure product reconstitution before use and disinfection. At time of dispensing, patients will be also provided with a separate biweekly ancillary kit containing sterile wipes and sterile pipettes for drug product administration. Patients will be provided with detailed instruction reporting the kit composition and procedures for product reconstitution and administration.

At visit 1 (Screening visit) eligible patients will be instructed by study personnel how to prepare and administer the Study Product (vehicle) eye drop solution and the first eye drop of the Study Product (vehicle) will be applied in both eyes at the site by the Investigator. The Investigator will document the first administration of the Study Product (vehicle) in the patient's medical record following Visit 1 to confirm the first administration of the Study Product (vehicle). Depending on the time of the subject's Screening visit, all doses may not be administered on this day. At visit 1, the study personnel will give the patient the 2-weekly boxed supply of the Study Product (vehicle) (CCI vehicle with diluent); patients will also receive a separate ancillary administration kit containing sterile pipettes and sterile disinfectant wipes for product reconstitution. Patients will be instructed to then self-administer at home the Study Product (vehicle) one drop 3 times a day in both eyes, approximately every 6 hours. The patient should bring the 2-weekly supply box home as soon as possible and store it at CCI °C, keeping it away from direct sunlight/heat.

During the Run-In period, patients will instill one drop of the solution (vehicle) in both eyes TID (approximately every 6 hours), starting in the morning when they wake up, for a total duration of 12±2 days. The contents of each vial are for daily administration to both eyes only for a given day. Agitation of the reconstituted product may cause foaming, hence should be avoided at any time. After the last administration for the day, the used vial should be returned to the original box and is not to be reused. The used/unused Study Product vehicle vials should be returned to the site at the end of the Run-In period (V2). The patient will bring them to the site during the Visit 2 and they will be checked by independent personnel not directly involved in study activities. The vehicle is not to be instilled on the day of the Baseline visit (Visit 2).

At Visit 2 (baseline visit- Day 1), the study personnel will give to the randomized patient the biweekly boxed supply of the Study Product (IMP or vehicle, CCI Study Product with diluent). The patient should bring the IMP, a biweekly supply box, home as soon as possible and store it at CCI °C, keeping it away from direct sunlight/heat. At Visit 2 (Baseline) patients will also receive a separate ancillary kit containing sterile pipettes and sterile disinfectant wipes. Further spare ancillary kit components could be provided to ensure product administration. IMP ophthalmic solution preparation and instillation instructions will

be provided to the patients.

Patients will instill one drop in both eyes three times a day (TID) (approximately every 6 hours), starting on Day 1 (Baseline visit) and continue the treatment for the next 2 weeks. Depending on the time of the subject's Baseline visit, it is reasonable and possible that all doses may not be administered on this day. The contents of each vial are for daily administration to both eyes only for a given day. After the last administration for the day, the used vial should be returned to the original box and is not to be reused.

After 2 weeks during Visit 3 (Study Product pick-up visit - Day 13±1) patients will return the used/unused study product vials to the site to be checked by independent personnel not directly involved in study activities. During the same Visit 3 patients will collect a second IMP 2-weekly kit and a separate ancillary kit.

At visit 4 the used/unused study product vials will be returned to the site by the patients to be checked by independent personnel not directly involved in study activities.

In summary, patients will return the used/unused study boxes/vials to the site personnel in this order: Study Product (vehicle) from the Run-In period at the baseline visit (Visit 2), the 2-weeks study product (IMP or vehicle) at mid-treatment visit (Visit 3), the second 2-weeks study product (IMP or vehicle) treatment at end-of-treatment visit (Visit 4).

At the scheduled visits (Baseline, weeks 2, week 4 and week 8), the Patient Diary will be reviewed by the Investigator with the patient for completeness and adherence to treatment. Missing information should not be provided during the Patient Diary check but reported as missing.

6.4 PARTICIPANT ASSIGNMENT, RANDOMISATION AND MASKING

6.4.1 Participant Assignment

Each patient who provides written consent to participate in this study will be assigned a unique 5-digit PID number (e.g., 01-001) consisting of a 2-digit study center number followed by the 3-digit screening number assigned sequentially by each study center, from 001 to 100. eCRF should be completed for each patient that signed the informed consent, including the screening failures.

6.4.2 Randomization

Interaction Response Technology (IRT) will be used to randomize the patients in a 1:1:1 ratio to each of the treatment arms.

Eligible patients will be randomized in a 1:1:1 ratio to rhNGF  mcg/mL TID (about 97 patients), rhNGF  mcg/mL TID (about 97 patients) or vehicle ophthalmic solution TID (about 97 patients). Patients in the vehicle arm will be randomly assigned 1:1 to two different vehicle filling volumes to preserve masking. Nevertheless, all the patients randomized to the vehicle arm will be analyzed as a single treatment arm.

Each randomized patient will be allocated with a randomization number, according to the stratified randomization list. Drop-outs after randomization will not be replaced.

Randomization will be stratified by site to ensure balanced assignment across treatment groups within each site. The stratified permuted block randomization list will be generated with a computer procedure by an independent statistician not involved in the conduct of the study.

Each Patient kit number will be randomly associated with a treatment group. The randomization list will be provided to the facility responsible for IMP packaging/labeling for the purpose of IMP preparation.

The enrollment of patients will be scheduled in order to assure an inclusion of approximately 291 patients to ensure at least 276 evaluable patients assuming up to 5% dropout rate.

6.4.3 Masking and Unmasking Procedure

Appearance, including packaging and labeling, of the study products (IMP or vehicle) will not allow recognition of the actual treatment. Masked information on the identity of the assigned study products will be provided for each patient.

Unmasking can only occur in case of emergency when knowledge of the treatment identity is essential for treating the subject. If the treatment code needs to be broken in the interest of patient safety for a medical emergency, the Investigator is allowed to break the treatment code for the specific patient, even before informing the Sponsor. The Investigator must always notify the Sponsor, so that the reason for any premature unmasking can be documented, by means of a communication to CRO/Dompé Global Pharmacovigilance, Safety and Surveillance to the contact details in the section “[CONTACT INFORMATION](#)” and to Dompé Medical Expert. The Investigator will inform the Dompé representative (Dompé Medical Expert) if an emergency unmasking was performed without revealing the treatment identity, in order to avoid a dissemination of unmasked information.

Dompé shall be responsible to prepare and submit annual safety reports (Development Safety Update Report – DSUR) to relevant Regulatory Authorities in the countries concerned, as per applicable requirements.

Additionally, Dompé Global Pharmacovigilance, Safety and Surveillance shall unmask the patient's treatment if a reported SAE meets criteria of a Suspected Unexpected Serious Adverse Reaction (SUSAR) in order to fulfill expedited regulatory reporting requirements. Unmasked information shall not be disclosed to Investigators or to Dompé and CRO Clinical Research staff. Specifically, the identity of the IMP treatments will remain unknown to the patient, Investigator, site staff, Dompé's clinical research personnel and CRO staff (apart from pharmacovigilance).

Unmasking events will be recorded and reported in the final study report.

6.5 TRIAL INTERVENTION COMPLIANCE

All patients enrolled in the trial will receive a Patient Diary at the screening visit (day -12±2), at the baseline visit (day 1), and at the end-of-treatment visit (week 4). The patients will be required to fill these diaries logging their use of the supplied drug (Study Product vehicle/IMP/NIMP). These Patient Diaries will be reviewed by the Investigator with the patient for completeness at the scheduled visits (baseline, weeks 2, 4 and 8). The data from the Patient's Diary will be entered in the eCRF as well.

Starting from the first IMP administration done at the baseline visit until the last expected administration (considering 1 drop TID, i.e. 3 drops per day), compliance for the study eye will be derived as the proportion (%) between the actual number of drops administered in the study eye and the expected number of drops in the study eye as if the subjects completed the study (up to 84 drops depending on the date of treatment completion status collected in the eCRF; for patients who prematurely discontinue the treatment, the expected number is set to 84). Further details will be inserted in the SAP.

Assessment of the IMP accountability will be made by determining the number of Study Medication vials (CCI product) dispensed to the patient at Baseline/V2 and at Week 2/V3 and the number of unused Study Medication vials returned at Week 4/V4 (EOT). The number of used and unused vials of diluent will also be collected.

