
Information	Description
	
not an exclusion criterion but must be removed and discontinued at the screening visit).
 
17. Medical history of drug addiction or alcohol abuse (>1 drink /day for women and >2 drinks /day for men following USDA dietary Guidelines 2020-2025).
 
18. Any prior ocular surgery including but not limited to amniotic membrane transplant, refractive (PTK/LASIK/Epi-LASIK/LASEK/SMILE), palpebral, cataract surgery, trabeculectomy, vitrectomy and pan-retinal photocoagulation (PRP) within 90 days before the screening visit.
 
19. Participation in a clinical trial with a new active substance, including medical devices, during the previous 60 days.
 
20. Participation in another clinical trial study at the same time as the present study.

Study Medication, Dosage and Mode of Administration	
The route of administration for the study products is ophthalmic with the administration applied in both eyes.
 
The IMPs consist in a new formulation to be reconstituted daily by the patients (kit containing CCI rhNGF + diluent for reconstitution) for topical ocular administration at the following concentrations of active ingredient:
 
 IMP 1: rhNGF C mcg/mL IMP 2: rhNGF C mcg/mL IMP (vehicle): rhNGF 0 mcg/mL 
During the treatment period, the IMPs are administered according to the following scheme:
 
 - IMP 1: One drop of rhNGF C mcg/mL instilled in both eyes TID (every approx. 6 hours). - IMP 2: One drop of rhNGF C mcg/mL instilled in both eyes TID (every approx. 6 hours). - IMP (vehicle): One drop of Vehicle instilled in both eyes TID (every approx. 6 hours). 
A bi-weekly kit will be provided to the patient at the time of baseline (visit 2) and week 2 (visit 3) visits. An ancillary kit containing sterile pipettes for vials adapter and sterile wipes will be provided at the same time. In addition to that, for the Run-In period a bi-weekly kit of vehicle will be given to the patients, and for all the Follow-Up period the Sponsor will also supply preservative free artificial tears (AT).

Duration of Treatment	
Four (4) weeks (28 Days±1) of treatment with IMPs according to the randomization list.

Primary Efficacy Endpoint	
The primary efficacy endpoint is the mean change from baseline to Week 8 in symptoms of dry eye assessed by SANDE Global Score [Time Frame: week 8 (V5)].

Information	Description

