3.6. Definition of Study Eye

The Study Eye is the worst eye: assuming that all the inclusion/exclusion criteria are met in both eyes, the worst eye (Study Eye) will be determined at the baseline visit based on the lower Schirmer I (without anesthesia) score. If the Schirmer I score of both eyes is identical, the Study Eye will be determined based on the CCI. If both eyes are identical even considering NEI, then simply the right eye will be considered as the Study Eye.

4. General Statistical Considerations

Tabulations of summary statistics, graphical presentations, and statistical analyses will be performed with SAS® software, version 9.4 or higher.

Descriptive statistics for continuous variables in summary tables will include the number of patients in the analysis (n), mean, standard deviation (SD), median, first quartile (Q1), third quartile (Q3) and range (minimum, maximum). Descriptive statistics for qualitative variables in summary tables will include counts and percentages per category. If appropriate, 95% confidence intervals (CIs) around the mean or the proportion will be presented. The number of patients with missing data will be presented under the “Missing” category. Missing values will not be included in the denominator count when computing percentages. When continuous data are summarized, only the non-missing values will be evaluated for computing summary statistics. Any exception will be declared.

In general, regardless the strategy of the analysis described in [Section 8](#), a summary table with descriptive statistics will be produced for each efficacy endpoint. Summaries will be generated for observed cases, on absolute values and changes from baseline at each timepoint for continuous variables, on proportions at each timepoint for qualitative variables.

For the purpose of efficacy analyses in this trial, the statistical analysis (both descriptive and inferential) will be done on the Study Eye which is determined at baseline visit (visit 2). Details will be provided in the statistical analysis outputs as notes. In case the analysis involves both eyes, it will be clearly declared. This consideration only applies to the assessments that are done at individual eye level and does not apply to any assessment done at patient level (e.g., SANDE, CCI ...).

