5.2. Protocol Deviations

Protocol deviations (PDs) that will be analyzed and reported in the TLFs come from two different sources: CTMS and SAS programming. All PDs will be reviewed in a masked manner before the hard lock of the database in order to check the ones that actually have an impact (e.g. bias) on the statistical analysis. PDs will be classified for analysis purposes in Major and Minor PDs according to the level of bias that they can produce on the primary and/or key secondary endpoints. Not all deviations reported in the CTMS will be analyzed (i.e. will not be classified as either major or minor PDs), if not relevant from an analysis perspective. Major PDs will define patients that will be excluded from the PP set.

Major protocol deviations derived in SAS:

The following PDs will be derived in SAS and classified as major. Any further change, if any, will be discussed and documented during the blind DRM.

- Lack of compliance with IMP (compliance <80% or compliance >120%).
- Exposure to IMP lower than expected (exposure in days < 24 days).
- Missing all post-baseline assessments for one or more of the primary and key secondary endpoints (subjects should have at least one post-baseline assessment for each of the primary and key secondary endpoints).
- Intake of prohibited medications.

Minor protocol deviations derived in SAS:

- Lack of compliance with NIMP (compliance <80% or compliance >120%).

Finally, number of patients with at least one major/minor PD will be summarized. Major PD will be tabulated, while all PDs (major and minor) will be listed, including full description and the GCP severity classification, as reported in the PD rule document (significant / not significant). Tabulation and listing will be based on all randomized patients.

6. Demographics and Baseline Characteristics

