- MMRM described in [Section 8.1.1](#) will be applied to Per-Protocol Set based on the same imputed dataset described in [Section 8.1.1](#).

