9.1. Adverse Events

An Adverse Event (AE) is defined as any untoward medical occurrence in a patient or clinical investigation patient administered a medicinal product and which does not necessarily have a causal relationship with this treatment. An AE can therefore be any unfavorable and unintended sign (including an abnormal laboratory finding), symptom, or disease temporally associated with the use of a medicinal product, whether or not related to the medicinal product.

Treatment-emergent AEs (TEAEs) are defined as AEs that are reported or worsened on or after the first dose of IMP.

Adverse events will be coded according to latest version of MedDRA. Unless otherwise specified, AEs will be summarized by treatment arm and by SOC and PT, with SOC sorted in descending order of patient incidence and PTs within each SOC in descending order of patient incidence in Total group, for each treatment period (“On Treatment period”, “On Follow-up period” and “Overall”). If the total frequency for any 2 or more PTs is equal, the PTs will be presented in alphabetical order.

When summarizing the number and percentage of patients with an event, patients with multiple occurrences of the same AE or a continuing AE will be counted only once. Patients will be presented according to the highest severity (the strongest relationship) in the summaries by severity (of related AEs), if patients reported multiple events under the same SOC and/or PT.

Ocular TEAEs will be summarized separately from non-ocular TEAEs. Ocular TEAEs will be summarized for the Study Eye and the fellow eye. Non-ocular TEAEs will be summarized regardless of the Study Eye or the fellow eye.

By-patient listings of ocular and non-ocular AEs will be presented by treatment and ordered by site.

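### Per Protocol compliance counts Study Eye drops only, yet the one specified Per Protocol analysis is of SANDE, a patient-level score after dosing both eyes, so missed fellow-eye drops go unseen

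*Protocol*

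**What the plan says.** Protocol 6.3 has patients dose both eyes three times a day. Protocol 6.5 measures adherence in one of them: "compliance for the study eye will be derived as the proportion (%) between the actual number of drops administered in the study eye", divided by the number expected in that eye. SAP 7.3.1 also derives IMP compliance for the Study Eye, from administrations recorded in the electronic diary.

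That figure decides Per Protocol membership. Protocol 11.6 excludes patients below 80% or above 120%, and SAP 5.2 lists as a major deviation "Lack of compliance with IMP (compliance <80% or compliance >120" (per cent). SAP 7.3.1 gives the same limits for Per Protocol exclusion but words them in terms of accountability, which SAP 7.3.2 counts in vials.

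The use of the set is narrow. Protocol 10.6.3 names a Per Protocol repeat of the primary analysis. SAP 8.1.2 says that the SANDE MMRM "will be applied to Per-Protocol Set based on the same imputed dataset". The readable SAP specifies no Per Protocol analysis of Schirmer-I or corneal staining. SAP 4 says that its convention of analysing the Study Eye "does not apply to any assessment done at patient level (e.g., SANDE" is the first example it gives).

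**The concern.** A Per Protocol analysis should show the effect in patients treated as planned. Here the plan is treatment of both eyes and the outcome is a symptom score for the whole patient, to which either eye can contribute. An adherence filter that looks at one eye does not match that outcome. It can label a patient with a wholly untreated eye as fully compliant.

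One-eye stopping is plausible in this setting. Protocol 6.2 reports eye pain in 48%, up to 63.5%, and 42% of patients in three earlier dry eye studies. Inclusion criterion 3 asks only that the same eye meet all the clinical features, so the fellow eye may be milder. Neither fact gives a rate of one-eye dosing.

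At stake is how to read one sensitivity analysis: whether agreement between it and the primary result says what it appears to say about patients who followed the regimen.

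**Working it through.** **Inputs**
- Frequency per eye: "considering 1 drop TID, i.e. 3 drops per day" (Protocol 6.5).
- Duration: "Four (4) weeks (28 Days±1) of treatment with IMPs" (Protocol 1.1).
- Stated denominator: "up to 84 drops depending on the date of treatment completion status collected in the eCRF" (Protocol 6.5).
- Limits: 80% and 120% (Protocol 11.6, SAP 5.2).

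**The plan's own figure.** 3 drops/day × 28 days = 84 drops in the Study Eye, as stated. Both eyes: 2 × 84 = 168.

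**Rule as written against the whole regimen.** Written rule = 100 × Study Eye drops / 84. Share of plan = 100 × (Study Eye + fellow-eye drops) / 168.

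| Study Eye | Fellow eye | Written rule | Share of plan | Per Protocol set as written |
|---|---|---|---|---|
| 84 | 84 | 100.0% | 100.0% | kept |
| 84 | 0 | 100.0% | 50.0% | kept |
| 68 | 0 | 81.0% | 40.5% | kept |
| 42 | 42 | 50.0% | 50.0% | excluded |

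The third row is the lowest total that the drop rule retains, since 67/84 = 79.8% falls below the limit. The last row shows that the gap concerns the fellow eye only.

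**Do the other numerical rules catch the second row?**
- Vial accountability (SAP 7.3.2): one vial serves both eyes for a day (Protocol 6.3). Two kits of 14 make 28 vials, and a patient dosing one eye every day returns none unused: (28 − 0)/28 = 100%. Not caught.
- Exposure under 24 days (SAP 5.2): calculated from the first and last treatment dates (SAP 7.3.1). Not caught.

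**Possible size.** The documents give no rate of one-eye dosing and no effect in such patients. Assume, for illustration, that they make up 1-5% of an active arm, that half of the planning effect is lost in them, and that the vehicle arm is unaffected. The planning effect is 28.2 − 17.4 = 10.8 points (Protocol 10.1).
- Dilution: 10.8 × 0.5 × 0.01 = 0.05 points, to 10.8 × 0.5 × 0.05 = 0.27 points.
- Standard error of the difference with the planning SDs and 92 per arm: √((26.36² + 20.29²)/92) = 3.47.
- Largest case: 0.27/3.47 = 0.08 standard errors.

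**The case against.** The strongest defence is that the 80-120% rule is not the only way out of the Per Protocol set. Reasons for exclusion are settled at the masked Data Review Meeting from a list that is expressly not exhaustive. Deviations also come from the trial management system and are graded by the bias they could cause. Protocol 4.1 makes a different dosing frequency a deviation. A patient who stopped dosing one eye could therefore be classed as major. This stands: a reader might infer that such patients are bound to be kept, and the documents do not say so. What remains is that no written rule requires their exclusion.

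Study Eye compliance is also a reasonable choice for the three key secondary endpoints, which are all Study Eye measures, and SAP 5.2 grades deviations against primary and key secondary endpoints together. That explains the rule, but no Per Protocol analysis of those endpoints is specified.

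SAP 4 concerns which eye's efficacy assessments are analysed, not compliance. It shows that SANDE is patient-level; it does not make the SAP contradict itself.

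Parts of SAP 7.3.1 are redacted, including text around the expected and actual counts. The rule that extra administrations count only if given in the study eye suggests diary recording by eye. However, the one diary question quoted, on artificial tears, names no eye, so by-eye recording needs confirming. Protocol 6.5 is readable and limits compliance to the Study Eye.

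**Conclusion.** The point holds as a mismatch between a stated rule and the one analysis it serves. A patient whose missed drops are all in the fellow eye can be 100% compliant with 50% of the planned drops.

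Three stronger readings are not supported:
- That anyone taking half the drops passes. Spread evenly over both eyes, half the drops gives 50% and exclusion.
- That the primary result is at risk. It rests on the Full Analysis Set, which does not use compliance. Protocol 10.6.3 makes the sensitivity analyses conditional on a significant primary comparison. SAP 8.1.2 opens with the same condition, although it lists the Per Protocol analysis in a later group without repeating it.
- That fellow-eye safety results cannot be interpreted. The SAP says "Ocular TEAEs will be summarized for the Study Eye and the fellow eye", but those tables use the safety population and do not depend on compliance.

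The effect is probably small: under 0.1 standard errors in the illustration, which rests on assumed inputs, and in the direction of a smaller Per Protocol difference. The case for acting is that the rule misclassifies patients and is cheap to correct.

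**What to change.** In SAP 5.2 and 7.3.1, and in Protocol 6.5 and 11.6 to match:
1. Confirm that the diary records doses by eye.
2. If it does, derive IMP compliance for each eye and require both to lie within the existing 80-120% limits for the Per Protocol set used with SANDE.
3. If it does not, list known non-dosing of the fellow eye as a pre-specified major deviation.
4. Reconcile the basis for exclusion: Protocol 11.6 and SAP 5.2 say compliance, while SAP 7.3.1 says accountability. Vial counts cannot detect one-eye dosing.

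The cost is wording, one further derivation if by-eye data exist, and a slightly smaller Per Protocol set. Showing fellow-eye compliance beside the fellow-eye adverse event tables is optional.
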